2.7 Benefit-risk assessment of LCI699 in study population

Potential patient benefits

There is an unmet medical need in patients with Cushing's disease which is a rare and serious disease with limited options for medical therapy. A proof-of-concept study ([\[LCI699C2201\]](#) Part 1) in 12 patients with uncontrolled Cushing's disease showed that 11/12 patients had a normal mean UFC at the end of 10 weeks of LCI699 therapy. Continuation of the amended study ([\[LCI699C2201\]](#), Part II core) showed that 15/19 (79%) patients had normal mean UFC levels at the end of 22 weeks of LCI699 therapy; there was a trend toward improved fasting glucose and HbA1c in patients with diabetes at baseline, and an improved fasting lipid profile in patients with dyslipidemia at baseline. Based on these results LCI699 is a promising potential new therapy in patients with uncontrolled Cushing's disease who have failed or are unable to receive primary surgical therapy

Study-specific risks

Study-specific risks in study [\[LCI699C2301\]](#) include: the potential for prolonged periods of uncontrolled hypercortisolism during the screening period while prior cortisol-lowering therapy is washed out. The duration of washout ranges from 1-8 weeks for nearly all drugs, and 6 months for mitotane. For patients who begin the study on a medication that requires a washout periods

of ≥ 4 weeks, it is possible to switch to a medication with a short washout period (e.g., 1 week) until the last part of the washout. Patients randomized to the placebo arm during the randomized withdrawal period may also experience uncontrolled hypercortisolism for up to 8 weeks duration (Week 26 to Week 34); this risk is mitigated by the “rescue” procedure, in which patients with mean UFC $> 1.5 \times$ ULN (with at least 2 of the 3 individual UFC levels $> 1.5 \times$ ULN) during the randomized withdrawal period are discontinued from randomized withdrawal and changed to open-label treatment with LCI699.

Risks of LCI699 treatment in study population

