4.1.3.7 Monitoring and dosing guidelines on resuming open-label LCI699

Patients that are discontinued from randomized withdrawal due to lack of efficacy as described in [Section 4.1.3.6](#), will resume open-label LCI699 at the time of discontinuation, which will typically occur before Week 34. Patients that are not discontinued during randomized withdrawal will resume open-label LCI699 at the end of randomized withdrawal (Week 34) and thereafter (Study Period 4).

Precaution

The investigator is advised to monitor patients closely upon resuming open-label LCI699, which may occur either during the randomized withdrawal period (if the patient is discontinued from randomized withdrawal), or at Week 34 (if the patient was not discontinued from randomized withdrawal). Week 34 is the time of entry into Study Period 4. Some patients may experience a period of instability with respect to UFC levels and symptoms. In particular, patients with uncontrolled UFC may experience glucocorticoid withdrawal syndrome if UFC is reduced (corrected) too rapidly. Unscheduled visits are permitted as often as needed until UFC stabilizes. In addition, local laboratory results may be used to guide treatment decisions, but all UFC tests must be sent to the central laboratory for later confirmation. This is the only time during the study in which local laboratory results can be used for LCI699 dose decisions.

Upon resuming open-label LCI699, the investigator has the discretion to select the dose, and is advised to consider the following guidelines:

- Patients with a normal UFC during randomized withdrawal should resume the same dose of study drug on re-starting open-label LCI699.
- Patients with uncontrolled UFC that were discontinued from randomized withdrawal are at increased risk of developing glucocorticoid withdrawal syndrome.
 - LCI699 could be prescribed at the same dose that was used at Week 26
 - Alternatively, LCI699 could be prescribed at a lower dose than the one used at Week 26, to reduce the risk of glucocorticoid withdrawal syndrome. With this strategy, it is expected that the dose will need to be titrated upward.
 - It is not recommended to prescribe a dose higher than was used at Week 26, because there may be an excess risk of glucocorticoid withdrawal syndrome, hypocortisolism or adrenal insufficiency.
- Patients whose dose was reduced for safety reasons during the randomized withdrawal period should resume the reduced dose of study drug on re-starting LCI699.

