10.5.3 Safety objectives

10.5.3.1 Analysis set and grouping for the analyses

Analysis set and treatment groups (see [Section 10.1](#) and [Section 10.3](#)) used for safety analyses will be described below:

- For study period up to Week 26: SAS by All patients only.
- For randomized withdrawal period: SASR by LCI699 group and Placebo group
- For overall study period while on LCI699: SAS by LCI699 group, Placebo group, Non-randomized patients, and all patients.
- In addition to the above mentioned analysis, other post-treatment safety data collected will be included in listings and flagged as appropriate.

The overall observation period will be divided into three mutually exclusive segments:

1. pre-treatment period: from day of patient's informed consent to the day before first dose of study medication
2. on treatment period: from day of first dose of study medication to 30 days after last dose of study medication
3. post-treatment period: starting at day 31 after last dose of study medication

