*If protocol deviation happens before Week 24, when the key secondary endpoint is assessed

**If protocol deviation happens before end of randomized withdrawal period, when the primary endpoint is assessed

The analysis sets used for various analyses in the Final CSR are summarized below

Table 2-4 Analysis sets used for specific analyses

	FAS	SAS	PPFAS/ PPRAS
Patient Disposition	X		
Demography and baseline disease characteristics	X		
Medical History	X		
Prior Medication	X		
Protocol Deviation	X		
Concomitant Medications		X	
Exposure to study medication		X	
Efficacy analyses	X		X*
Safety analyses		X	
Patient-reported outcomes	X		
* PPFAS will only be used in supportive analyses for key secondary efficacy endpoint. * PPRAS will only be used in supportive analyses for primary efficacy endpoint.			

When appropriate, patients in a given analysis set could be classified into mutually exclusive treatment groups as described below:

For patients in PPRAS

- LCI699 group: patients randomized to continued treatment of LCI699 for the randomized withdrawal period of the study
- Placebo group: patients randomized to placebo for the randomized withdrawal period of the study

For patients in FAS/PPFAS

- LCI699 group: patients randomized to continued treatment of LCI699 for the randomized withdrawal period of the study
- Placebo group: patients randomized to placebo for the randomized withdrawal period of the study
- Non-randomized patients: patients who do not enter randomized withdrawal period of the study (either discontinued study before the randomization or not eligible to be randomized)

For patients in SAS

- LCI699 group: patients receiving study treatment of LCI699 for the randomized withdrawal period of the study
- Placebo group: patients receiving study treatment of placebo for the randomized withdrawal period of the study
- Non-randomized patients: patients who do not enter randomized withdrawal period of the study (either discontinued study before the randomization or not eligible to be randomized)

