2.7 Analysis of secondary efficacy objectives

For the objectives identified below, the definition of Baseline/Randomization assessment and the method of computing confidence intervals are specified in Section [2.1.1.2](#) and Section [2.1.1.8](#) respectively. Last observation carried forward (LOCF) method will not be used in any of these analyses. For analysis using FAS, results will be presented by LCI699 group, Placebo group, Non-randomized patients, and All patients.

2.7.1 Compare the time-to-last control of mUFC during the randomized withdrawal period between patients randomized to continued LCI699 and placebo

The results of this objective were reported in the interim CSR, and will not be repeated for the Final CSR.

2.7.2 Assess the complete, partial, and overall response rate at Week 12, Week 24, Week 48, and during the extension period

The proportion of complete responders (enrolled patients with $mUFC \leq ULN$), partial responders (enrolled patients with $mUFC > ULN$ and at least 50% reduction from baseline), and overall responders (enrolled patients with $mUFC \leq ULN$ or have at least 50% reduction from baseline) will be summarized using point estimates for every scheduled visit in the core and extension (provided [adequate follow-up](#)) at which UFC is collected. 95% 2-sided CIs for response rates will be provided for Week 48, Week 60, Week 72 and the last available assessment of the study. The FAS will be used for the analyses.

2.7.3 Assess the change in mUFC during the core and extension period of study

For the actual value and change in mUFC from baseline during the overall study period, descriptive summaries will be provided for every scheduled visit in the core and extension (provided [adequate follow-up](#)) at which UFC is collected. The FAS will be used for the analysis.

Patients randomized to placebo during the RW period, will not have their mUFC values included in the analysis for visits at which they received placebo.

2.7.4 Assess the change in cardiovascular-related metabolic parameters associated with Cushing's disease during the core and extension period of the study

The following parameters will be analyzed: glucose, HbA1c, fasting lipid profile, SBP, DBP, weight, waist circumference and BMI).

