2.8 Safety analyses

The assessment of safety will be based mainly on the frequency of adverse events and on the number of laboratory values that fall outside the pre-determined ranges. Other safety data (e.g. electrocardiogram, vital signs, and special tests) will also be presented.

In the Final CSR results for the overall study period will be analyzed, using the SAS. Results will be presented by Randomized patients, Non-randomized patients and All patients.

The safety results for the Final CSR will focus solely on the safety of LCI699. Therefore scheduled safety assessments performed whilst on placebo, for patients randomized to placebo during the RW period, will not be included. Similarly, adverse events with a start date which corresponds to when a patient was receiving placebo will not be included in adverse event summaries.

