3.2 Power consideration for analysis of key secondary objective

The analysis of the key secondary objective will be based on the 2-sided 95% confidence interval constructed using the Clopper-Pearson exact method. If the lower bound of this 95% confidence interval is $\geq 30\%$, the null hypothesis will be rejected and the complete response rate will be considered at least 30% after 24 weeks of treatment with LCI699.

The above testing on the key secondary objective will only be carried out if the null hypothesis for the primary objective is rejected. This sequential procedure will ensure preservation of the overall 2-sided type 1 error at 5%.

Assuming a 50% complete response rate (mUFC \leq ULN) at end of 24 weeks of LCI699 treatment, for 132 enrolled patients, there is 99.7% chance that the lower bound of 95% 2-sided CI of observed response rate (based on Clopper-Pearson Exact method) is larger than 30.0%.

4 Change to protocol specified analyses

5 Reference

American Diabetes Association, (2010), 'Diagnosis and Classification of Diabetes Mellitus', *Diabetes Care*, 33, Supplement 1, S62-S69.

Dolan P (1997), Modeling valuations for EuroQol health states, *Med Care*, 35:1095-108.

FDA PRO Guidance (2009) <https://www.fda.gov/downloads/drugs/guidances/ucm193282.pdf> retrieved 27/07/2017

McClure, Nathan S., et al. (2017), "Instrument-defined estimates of the minimally important difference for EQ-5D-5L index scores", *Value in Health*, 20.4: 644-650.

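### SAP 2.8 merges the two randomized arms in the Final CSR safety tables, unlike protocol 10.5.3.1, so safety after restarting LCI699 cannot be read by arm from those summaries

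*SAP*

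**What the plan says.** SAP 2.8 covers the overall study period in the safety set and gives the columns as "Results will be presented by Randomized patients, Non-randomized patients and All patients". It explains that the Final CSR is concerned only with the safety of LCI699, and so drops scheduled assessments and adverse events that fall in placebo time.

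Protocol 10.5.3.1 sets a different layout for that period: "For overall study period while on LCI699: SAS by LCI699 group, Placebo group, Non-randomized patients, and all patients".

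The SAP's own definitions follow the protocol. Among the safety-set groups in SAP 2.2 is "Placebo group: patients receiving study treatment of placebo for the randomized withdrawal period of the study", listed apart from the LCI699 group. For efficacy, SAP 2.7 keeps the split: "For analysis using FAS, results will be presented by LCI699 group, Placebo group, Non-randomized patients, and All patients". SAP section 4, "Change to protocol specified analyses", is a heading with no entry in the supplied text.

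Protocol 4.1.3.7 advises close monitoring when open-label LCI699 is resumed: "Some patients may experience a period of instability with respect to UFC levels and symptoms". It names glucocorticoid withdrawal syndrome, and says patients taken out of randomized withdrawal for uncontrolled UFC are at increased risk of it. Patients whose UFC stayed normal also restart: "Patients with a normal UFC during randomized withdrawal should resume the same dose of study drug on re-starting open-label LCI699".

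SAP 2.8.1.6 tabulates AESIs by time of onset, with Week 26 to Week 48 as one window. The denominator is patients still on study when the window opens. No split by arm is stated.

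**The concern.** The two arms have different LCI699 histories after Week 26. One continues on drug. The other is off drug for up to 8 weeks (protocol 2.7) and then restarts. Restart is the moment the protocol singles out for caution, and hypocortisolism-related events are a named AESI group (protocol 8.1.3).

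The SAP's stated focus on LCI699 is a reason to remove placebo-time data. It is not a reason to pool the arms: the protocol grouping is already limited to time on LCI699 and still keeps them apart. Safety loses the split while efficacy keeps it, and no justification is recorded. At stake is whether a reader of the final summary tables can compare the arms after restart. The primary and key secondary results are not affected.

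**Working it through.** **Inputs.** Allocation is 1:1 (protocol 4.1.3.3). The plan has 33 per arm, with 70% against 30% response and 87% power at two-sided 0.05 (protocol 10.8). Placebo runs at most from Week 26 to Week 34. The documents give no AESI rates after restart, so the rates below are assumptions.

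**The plan's own figure.** It is used here only for arm size. The continuity-corrected normal power is Φ[(0.40 − 1/33 − 1.96·√(0.5/33)) / √(0.42/33)] = Φ[(0.3697 − 0.2413)/0.1128] = Φ(1.14) = 87.3%. Simulation of the exact stratified CMH test gives 87.6%. The stated 87% reproduces.

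**Dilution.** With equal arms the merged rate is (p_P + p_L)/2. Its excess over the LCI699 arm is (p_P + p_L)/2 − p_L = (p_P − p_L)/2, half the true arm difference whatever its size.

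| Assumed Placebo arm | Assumed LCI699 arm | Merged column | Excess by arm (points) | Excess left in merged column (points) |
|---|---|---|---|---|
| 10% | 5% | 7.5% | 5 | 2.5 |
| 20% | 5% | 12.5% | 15 | 7.5 |
| 30% | 10% | 20% | 20 | 10 |
| 40% | 10% | 25% | 30 | 15 |

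The last column presumes the reader knows the LCI699-arm rate. The merged tables do not give it.

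**The Week 26 to 48 onset window.** It is 48 − 26 = 22 weeks long. Placebo patients are in the denominator from Week 26, but events starting on placebo are excluded (SAP 2.8.1.3). If every placebo patient stayed on placebo for the full 8 weeks and nobody left, the randomized column would hold 66 × 22 = 1,452 patient-weeks, of which 33 × 8 = 264 could not contribute an event: 264/1,452 = 18%, or 8/22 = 36% of the placebo arm's time. These are upper limits, because patients who exit early return to LCI699 sooner. As an illustration, assume a constant hazard giving 10% over 22 weeks and no restart effect. The placebo arm would then show 1 − 0.9^(14/22) = 6.5%, and the merged column (10 + 6.5)/2 = 8.2%. So the merged rate is lowered as well as averaged. For response rates, SAP 2.1.1.7 removes placebo patients from the denominator at placebo visits; the onset table has no such rule.

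**What by-arm columns can show.** At 33 per arm, power for 20% against 5% is 45%, and for 30% against 10% it is 53%. Separate columns would be descriptive.

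**The case against.** A reader might infer that restart harm is hidden altogether. The documents do not support that. SAP 2.8.1 displays adverse events by patient and SAP 2.8.1.3 lists all of them, so arms can be reconstructed by hand. Every restart occurs by Week 34, so at least 14 weeks after it (48 − 34) lie in the core phase, which the interim CSR reported under a SAP dated 06-Jul-2018. Protocol 10.5.3.1 applies to that report, which may show the arms separately. This stands, with two limits: that SAP is not supplied, and the Final CSR uses the MedDRA version and AESI list current at its own lock (SAP 2.8.1.1, 2.8.1.5), so interim counts may rest on different definitions.

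The departure is also softer than a flat breach. The introduction to protocol section 10 directs its methods at the core study and extends them to the extension phase as appropriate, and SAP 2.2 introduces its groups as applying when appropriate. That gives latitude. But SAP 2.8 covers the whole study period, core included, and no reason for the merge is given.

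Restoring the protocol's columns would not by itself isolate restart events. Overall-period columns also contain 26 weeks of treatment before randomization and the long extension. That stands, and it is why the fix includes a table the protocol does not require.

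A reader might also infer that all 33 placebo patients restart, and that 33 × 0.70 ≈ 23 do so after losing control. Neither holds. Patients who leave the study during randomized withdrawal for other reasons do not receive open-label LCI699 (protocol 4.1.3.6). Non-responders include discontinuations, missing Week 34 mUFC, and mUFC above ULN that does not meet the exit rule. Nor is a comparison from each patient's own restart date protected by randomization, because early restart depends on outcome.

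**Conclusion.** The point holds as an unrecorded change of grouping with a real reporting cost. The Final CSR safety summaries merge arms that protocol 10.5.3.1 separates. An excess confined to the placebo arm after restart is roughly halved and cannot be read by arm from those tables. The Week 26 to 48 AESI table does not repair this, because its randomized column carries up to 18% placebo time from which events are excluded.

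The halving needs only near-equal arms. The event rates are illustrative: nothing in the documents shows that an excess exists or how large it would be. Whether the interim CSR already gives the by-arm view cannot be settled from what is supplied. The change should be made, but it is a matter of presentation and traceability.

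**What to change.** - In SAP 2.8, restore the four columns (LCI699 group, Placebo group, non-randomized, all) for the AE, SAE, AESI and laboratory tables.
- Show the AESI-by-onset tables in SAP 2.8.1.6 by randomized arm, with a footnote that placebo-time events are excluded while placebo patients remain in the Week 26 to 48 denominator.
- Add one AESI summary by randomized arm over a fixed Week 34 to Week 48 window, so that the window does not depend on restart date. Note beneath it that events after an early restart but before Week 34 fall outside it, and that patients who left the study do not contribute.
- If the merged column is also kept, record and justify it in SAP section 4 and point to where the core-phase report gives safety by arm.

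The cost is one extra column in tables already planned and one extra table. The groups are defined in SAP 2.2, the study was unblinded at the core database lock, and no new data are needed.

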2.8.1 Adverse events (AEs)

All information obtained on adverse events will be displayed by patient.

The number and percentage of subjects with adverse events will be tabulated by system organ class and preferred term. A subject with multiple adverse events within a body system is only counted once towards the total of this body system if no change in severity.

2.8.1.1 Coding of AEs

Adverse events are coded using the Medical Dictionary for Regulatory Activities (MedDRA) terminology. The latest version available at the time of database lock will be used.

2.8.1.2 Grading of AEs

AEs will be graded according to the NCI Common Terminology Criteria for Adverse Events (CTCAE) version 4.03.

The CTCAE represents a comprehensive grading system for reporting acute and late effects of cancer treatments. CTCAE v4.03 is graded by definition a 5-point scale generally corresponding to clinical severity (mild, moderate, severe, life-threatening, and death). This grading system inherently places a value on the importance of an event although there is not necessarily proportionality among grades (a Grade 2 is not necessarily twice as bad as a Grade 1).

For adverse events for which CTCAE grades are not available, grades 1 – 4 corresponding to the severity of mild, moderate, severe, and life-threatening will be used. CTCAE grade 5 (death) is not used in this study; rather, this information will be collected on the “End of Treatment” or “Study evaluation completion” eCRF pages

2.8.1.3 General rules for AE reporting

AE summaries will include all AEs starting on or after study day 1 (i.e. on or after the day of the first administration of study drug) but no later than AE summary cutoff defined in Section [2.1.1.9](#). All AEs before data cutoff date will be listed, including those that start before study day 1. AEs starting prior to study day 1 will be identifiable based on the AE start date displayed in the listings.

AEs will be summarized by presenting the number and percentage of patients having at least one AE, and having at least one AE in each body system/primary system organ class and for each preferred term using the most current MedDRA coding available prior to database lock. A subject with multiple occurrences of an AE will be counted only once in the AE category.

Separate AE summaries will be presented by primary system organ class, preferred term, and maximum CTC grade. A patient with multiple CTC grades for an AE will be summarized under the maximum CTC grade recorded for the event. In the summaries presented by grade, all AEs will be pooled regardless of whether they are CTC gradable or not. AEs with missing CTC grade will be summarized under “missing”.

The frequency of CTC grades 3 and 4 AEs will be summarized separately.

Any information collected (e.g. CTC grades, relationship to study drug, action taken etc.) will be listed as appropriate.

Adverse events with a start date which corresponds to when a patient was receiving placebo will not be included in adverse event summaries.

2.8.1.4 AE summaries

The following adverse event summaries will be produced:

- Adverse events, regardless of study drug relationship, by primary system organ class, preferred term and maximum CTC grade
- Adverse events, suspected to be study drug related, by primary system organ class, preferred term and maximum CTC grade
- Adverse events, regardless of study drug relationship, by preferred term
- Adverse events, suspected to be study drug related, by preferred term
- All deaths, by primary system organ class and preferred term
- Serious adverse events, regardless of study drug relationship, by primary system organ class, preferred term and maximum CTC grade
- Serious adverse events, suspected to be study drug related, by primary system organ class, preferred term and maximum CTC grade
- Serious adverse events, regardless of study drug relationship, by preferred term and treatment
- Adverse events leading to study drug discontinuation, regardless of study drug relationship, by primary system organ class and preferred term
- Adverse events requiring dose adjustment or study-drug interruption, regardless of study drug relationship, by primary system organ class and preferred term
- Adverse events requiring additional therapy, regardless of study drug relationship, by primary system organ class and preferred term
- Serious adverse events leading to study drug discontinuation, regardless of study drug relationship, by primary system organ class and preferred term

- Adverse events of Special Interest, regardless of study drug relationship, by category and preferred term
- Adverse events of Special Interest with suspected study drug relationship, by category and preferred term
- Adverse events of special interest leading to study drug discontinuation, regardless of study drug relationship, by category, and preferred term
- Adverse events of special interest requiring dose adjustment or interruption, regardless of study drug relationship, by category, and preferred term
- On-treatment deaths and serious adverse events by system organ class and preferred term
- Non-serious adverse events (threshold = 5%) by system organ class and preferred term

